*****1998 US NORMS*****
*****;

*CREATING SF-36 STANDARDIZED SCORES (0-1
00 Means/SD's from 1998 General Population)*;

pf_z=(pf-83.29094)/23.75883;
rp_z=(rp-82.50964)/25.52028;
bp_z=(bp-71.32527)/23.66224;
gh_z=(gh-70.84570)/20.97821;
vt_z=(vt-58.31411)/20.01923;
sf_z=(sf-84.30250)/22.91921;
re_z=(re-87.39733)/21.43778;
mh_z=(mh-74.98685)/17.75604;

*****;
* COMPUTE SAMPLE RAW FACTOR SCORES                               *;
* Z SCORES ARE FROM ABOVE                                       *;
* SCORING COEFFICIENTS ARE FROM U.S. GENERAL POPULATION        *;
* FACTOR ANALYTIC SAMPLE N=2393: HAVE ALL EIGHT SCALES         *;
*****;

praw=(pf_z * .42402)+(rp_z * .35119)+(bp_z * .31754)+(sf_z * -.00753)+
      (mh_z * -.22069)+(re_z * -.19206)+(vt_z * .02877)+(gh_z * .24954);

mraw=(pf_z * -.22999)+(rp_z * -.12329)+(bp_z * -.09731)+(sf_z * .26876)+
      (mh_z * .48581)+(re_z * .43407)+(vt_z * .23534)+(gh_z * -.01571);

[figure not shown]
*COMPUTE AGGREGATE STANDARDIZED SUMMARY SCORES*;

[figure not shown]
PCS = (praw*10) + 50;
MCS = (mraw*10) + 50;

label PCS='STANDARDIZED PHYSICAL COMPONENT SCALE-00'
      MCS='STANDARDIZED MENTAL COMPONENT SCALE-00';

run;
```

## Appendix J Classification of Events Reviewed by the Committee

## Appendix K Analysis Plan of the PFS-S Study

This appendix is the statistical analysis plan for the PFS-S sub-study.

### Pre-filled syringe with safety system (PFS-S)

Sarilumab has been delivered via prefilled syringes (PFS) in most of the Phase 3 studies.

[figure not shown]
The pre-filled syringe with safety system (PFS-S) is a modified version of the prefilled syringe aimed at preventing needle stick injury by either the patient or by a caregiver (professional or non-professional) performing the administration. The “safety system” consists of a sharps injury prevention feature, which can be described as a sheath that automatically covers the needle once the injection is completed and thus prevents needle stick injury and re-use.

Compared to PFS, PFS-S also includes:

[figure not shown]
- a rigid needle shield that encloses the soft rubber needle shield covering the needle
- a finger flange with an ergonomic design and a large piston rod

The following figures show the unused and used PFS-S. At the end of the injection when the plunger rod has been pushed into the syringe as far as it will go, the needle safety shield is activated which can be seen as the syringe is pulled away from the skin.

*Unused syringe*

*Used syringe with activated needle safety shield*

## Study design

This is a Phase 3, multicenter, worldwide, non-randomized, open-label, 1-arm, 12-week sub-study of the LTS11210/SARIL-RA-EXTEND study. The sub-study will only be performed in limited sites in selected countries.

Patients at participating sites who have been enrolled in the main study (LTS11210) for at least 24 weeks and are willing to participate in the sub-study will be enrolled in the sub-study. The entry into the sub-study (V101) will be at any scheduled visit in the main study from Visit 8 (Week 24) or after. Sarilumab 150 mg q2w PFS-S or sarilumab 200 mg q2w PFS-S will be used in the sub-study to replace the sarilumab 150 mg q2w PFS or 200 mg q2w PFS used in the main study. At the entry into the sub-study (V101), the patients/persons performing injections will be trained how to use the PFS-S, and the sub-study injection diary will be dispensed to replace the patient diary of the main study. All the procedures described in the sub-study are additional to the main study activities, unless specified to replace procedures in the main study.

The patient/person performing each sub-study injection will respond to 3 questions related to PFS-S use on the injection diary after each PFS-S injection. A “no” response to any of these 3 questions will be defined as a product technical complaint (PTC). For any PTC, the Investigator will complete a PTC form and will send this PTC form together with the PFS-S that triggered this PTC back to the Sponsor according to a predefined process. The patients should be instructed to keep any PFS-S associated with a PTC separately from other PFS-S, so it can be identified when returned to site at the end of sub-study. The sponsor will validate or invalidate the occurrence of a product technical failure (PTF), which is defined as a PTC that has a validated technical cause.

For patients receiving sarilumab 200 mg q2w PFS-S the dose can be reduced to 150 mg q2w PFS-S at any time during the sub-study duration if the defined criteria specified in the main protocol for dose reduction are fulfilled.

When the patients have completed the 12 weeks of the sub-study they will return to the clinic to complete Visit 102 (V102) in addition to the scheduled main study visit on that day. They will switch back to the main study and continue sarilumab treatment through PFS.

If the patient chooses to end the participation in the sub-study during the sub-study duration but to continue in the main study with IMP administration via PFS, the V102 should still be completed and the patient should switch back to take IMP administration through PFS on and after V102 per the patient’s IMP administration schedule.

If a patient discontinues Investigational Medicinal Product (IMP) permanently in LTS11210 during the sub-study, he/she should complete all procedures planned for V102 in the sub-study as well as the end of treatment (EOT) and post treatment follow-up visits in the main study (see flowchart in main study).

## Study objective

### *Primary*

To assess the usability of the sarilumab pre-filled syringe with safety system (PFS-S) when administered to patients with active Rheumatoid Arthritis (RA)

[figure not shown]
### *Secondary*

To document the safety of sarilumab 200 mg q2w PFS-S and sarilumab 150 mg q2w PFS-S.

## Determination of sample size

The sample size of this sub-study is based on empirical consideration. No formal sample size calculation is performed but an estimate of 120 patients included in this sub-study with up to 6 injections per patient will provide approximately 680 injections to evaluate PTF during the 12 weeks of the study assuming 5% drop-out rate.

## Study plan

All assessments planned to be performed at the scheduled main study visit that coincides with the sub-study visit, are described in the main study flow charts. Below flowchart specifies only:

- those actions that are additional to the scheduled main study visit in LTS11210
- those actions that replace an action in the scheduled main study visit in LTS11210 (for example, study drug dispensing of the PFS-S IMP format, instead of the main study IMP in PFS)

	Sub-study assessments	
VISIT	V101	V102
DAY	D1	D85 (+/- 3 days)
Week	Wk0	Wk12
Eligibility	X	
Written Informed Consent	X	
IVRS call to start / end sub-study participation	X	X
Training on use of the PFS-S	X	
Dispense PFS-S a	X	
Dispense sub-study injection diary b	X	
Collect / review sub-study injection diary b		X
PTC reporting		X
AE related to a PTC reporting c		X
Serum Sarilumab (PK) d	X	X
ADA d	X	X

a PFS-S dispensing will replace the scheduled IMP dispensing at the main study visit

b Sub-Study Injection Diary dispensing and review will replace the dispensing and review of the main study Patient Diary in the scheduled main study visits

c Refer to Section 10.4.1 in Protocol Amendment 9 for instruction of reporting AE related to PTC

d If the sub-study visit coincides with a PK and ADA sampling time point in the main study, no additional samples are required for the sub-study.

Each patient will participate in the sub-study for a period of 12 weeks from the first sub-study visit (V101) to the final sub-study visit (V102). At the time of V101, eligible patients will start receiving sarilumab 200 mg q2w PFS-S or sarilumab 150 mg q2w PFS-S, if they reduced the dose in the main study per protocol, for 12 weeks as replacement of original sarilumab PFS in the main study in addition to background disease modifying anti-rheumatic drugs (DMARDs) therapy, if any. There is no post-treatment follow-up specific to the PFS-S sub-study, as all patients except patients who discontinue IMP permanently in LTS11210 during the sub-study will switch back to the main study at V102. For patients who discontinue IMP permanently in LTS11210 during the sub-study, they should complete all procedures planned for V102 in the sub-study as well as the end of treatment (EOT) and post treatment follow-up visits in the main study. The last on-treatment sub-study visit for patients who complete the sub-study will occur at Day 85 (Visit 102). The sub-study will be considered completed when the last sub-study patient has completed V102.

### Statistical analysis procedures and method

The phrase ‘treatment group’ used throughout this appendix refers to the following device/dose groups (PFS-S sarilumab 200 mg q2w, PFS-S sarilumab 150 mg q2w, PFS-S sarilumab 200 mg

q2w to 150 mg q2w ). The baseline value is defined as the original baseline in initial/previous studies before LTS11210, as in the main study.

## Disposition of patients

Below describes patient disposition for both patient study status and the patient analysis populations for the sub-study only, unless otherwise specified.

- All screened patients are defined as those patients who signed the informed consent for the sub-study.
- All enrolled patients are defined as all patients with signed informed consent who met the eligibility criteria to enter into the sub-study.
- The Safety population consists of all enrolled patients who received at least one dose of the IMP administered via PFS-S during this sub-study.
- The PK population consists of all enrolled patients on stable dose of sarilumab (receiving the same dose of sarilumab without treatment interruption) at least 24 weeks prior to V101 until V102 who receive at least 1 dose of the IMP and at least one non-missing serum concentration value during this sub-study.

For patient study status, the total number of patients for each one of the following categories will be presented using a summary table:

- All screened patients (informed consent signed)
- Screen failure patients and reasons for screen failure (not eligible per eligible CRF page)
- Non-enrolled but treated patients
- Enrolled but not treated patients
- Enrolled and treated patients
  - Patients who had stable dose at least 24 weeks prior V101
- Patients who had dose reductions during the duration of the sub-study
- Patients who discontinued the sub-study treatment by main reason for discontinuation
  - Patients who discontinued the sub-study treatment but continues in the main study
  - Patients who permanently discontinued the study treatment during participation in the sub-study
- Status for returning to the main study (Yes/No)

For all categories of patients (except for the screened and non-enrolled categories), percentages will be calculated using the total of all enrolled patients as the denominator. Reasons and time to treatment discontinuation will be supplied in tables giving numbers and percentages.

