### **11.3 ANALYSIS POPULATIONS**

The safety population will consist of all enrolled patients who receive at least 1 dose or part of a dose of IMP administered via PFS-S during this sub-study.

Safety analyses will be performed on the safety population. Patient data will be analyzed according to the treatment actually received (200mg q2w PFS-S, 150mg q2w PFS-S, dose reduction).

The PK population will consist of all enrolled patients who receive at least 1 dose of the IMP and at least one non-missing serum concentration value.

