## **Efficacy (Device) analysis**

Data will be described for the 12 weeks of this sub-study using the safety population. The efficacy analyses will be performed using descriptive statistics and presented by treatment group.

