## ***Primary endpoint***

The primary endpoint is the number of validated PFS-S-associated PTFs.

The injection diary will include specific questions about PTCs. The person performing each sub-study injection will record the answers to these questions in the diary each time he/she performs an injection with a PFS-S.

The questions include:

1. Were you able to remove the cap?
  - Yes
  - NoIf no, please describe / explain:
2. Was the needle safety system activated?
  - Yes
  - NoIf no, please describe / explain:
3. Did the safety system entirely cover the needle?
  - Yes

- No  
If no, please describe / explain:

At Week 12 (Visit 102), the Investigator will review the diary, confirm with the patient whether there are any problems associated with the use of PFS-S and record the responses in the e-CRF.

If the answer is “no” to any of the questions stated in the diary, the patients will be asked to provide further details of the complaint and a PTC form will be completed by the investigator. The PTC form and the PFS-S associated with PTC will be sent to the Sponsor following the pre-defined process. The sponsor will validate or invalidate the occurrence of a PTF. If the PTF is ruled out, the event is considered as a failed drug delivery (FDD) that is defined as patient’s failure to administer the full dose at a given attempt.

In addition, another question will be asked in the diary to confirm whether the person who performed the injection was trained:

4. Was the person who performed the injection the person who was trained by the site staff?
  - Yes
  - No

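### The PFS-S sub-study counts device failures only in patients who received a dose by the device, and the SAP narrows the protocol's definition without recording the change

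*SAP*

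**What the plan says.** SAP Appendix K, Disposition of patients, defines the sub-study safety population as enrolled patients who "received at least one dose of the IMP administered via PFS-S during this sub-study". Protocol Appendix R, section 11.3, defines it as "all enrolled patients who receive at least 1 dose or part of a dose of IMP administered via PFS-S during this sub-study". The SAP's lists of modifications (section 1.5 under Amendment 9, and section 1.6) do not mention that partial doses have been dropped.

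Under Efficacy (Device) analysis the SAP states: "Data will be described for the 12 weeks of this sub-study using the safety population". Protocol Appendix R, section 11.4.2.1, likewise names the safety population for the primary endpoint. Neither document defines a separate device or attempted-use set.

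On the endpoint, the SAP says: "The primary endpoint is the number of validated PFS-S-associated PTFs". A negative answer to any of three diary questions is a product technical complaint (PTC), and the sponsor then decides whether it has a technical cause (a PTF). The first question is "Were you able to remove the cap" and the third is "Did the safety system entirely cover the needle". A complaint in which a PTF is ruled out becomes a failed drug delivery (FDD), defined as the patient's "failure to administer the full dose at a given attempt".

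**The concern.** The endpoints are defined per attempt, but the analysis set is defined per delivered dose. A cap that cannot be removed is a complaint, and possibly a PTF, from a syringe that delivered nothing. An FDD is by definition an attempt without a full dose. If such attempts are a patient's only use of the PFS-S, the patient falls outside the population in which PTFs, PTCs and FDDs are tabulated.

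Membership is then decided in part by the outcome being measured, and the error has one direction: it can remove failures but cannot add them. The primary objective is usability, and a failure that ends PFS-S use at the first attempt is informative about it. There is also a plain inconsistency, since the SAP and the protocol describe the same population differently and the change is not recorded.

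**Working it through.** **The plan's own figure.** Both documents expect about 680 injections from 120 patients, up to 6 injections each and 5% drop-out (SAP Appendix K, Determination of sample size; protocol Appendix R, section 11.1). 120 × 6 × 0.95 = 684, which agrees. This matches drop-outs contributing no injections. If drop-outs gave half their injections, the total would be 114 × 6 + 6 × 3 = 702.

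**Who is in and who is out, on a literal reading.**

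| Patient's PFS-S experience | Protocol 11.3 | SAP Appendix K |
|---|---|---|
| At least one full dose, plus any failures | in | in |
| Full dose given, shield not activated or needle not covered | in | in |
| Only partial doses | in | out |
| Only attempts with no drug delivered | out | out |

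The second row follows from the device description in SAP Appendix K: the shield activates once the plunger has been fully depressed. Failures under questions 2 and 3 can therefore follow a complete injection. The last row shows that restoring the protocol wording closes only part of the gap.

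**How many patients.** The documents give neither a failure rate nor a rate of leaving after a failure, so both are assumptions. Let p be the chance that an attempt delivers no dose, and q the chance that the patient leaves the sub-study after a failed attempt. With up to 6 attempts,

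P(no dose ever) = Σ (j = 1 to 5) p^j (1 − q)^(j−1) q + p^6 (1 − q)^5.

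For p = 1% and q = 0.5 this is 0.005 + 0.000025 + … ≈ 0.005025, and 120 × 0.005025 = 0.60 patients. Expected patients lost out of 120:

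| p | q = 0 | q = 0.1 | q = 0.5 | q = 1 |
|---|---|---|---|---|
| 0.5% | <0.00001 | 0.06 | 0.3 | 0.6 |
| 1% | <0.00001 | 0.12 | 0.6 | 1.2 |
| 2% | <0.00001 | 0.24 | 1.2 | 2.4 |
| 5% | <0.00001 | 0.63 | 3.1 | 6.0 |

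At q = 0 the formula reduces to 120 × p^6, and at q = 1 to 120 × p. For scale, if all 684 injections were attempted, the expected no-delivery failures would be 684 × p = 3.4, 6.8, 13.7 and 34.2. Not all of these would be validated as PTFs.

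**The case against.** Several points on the other side stand.

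- The population selects patients, not injections. One delivered dose among up to six brings in the patient and every failure, cap failures included.
- The design makes a never-dosed patient unlikely. The patient or caregiver practises under observation, the first dose is given at the site (protocol Appendix R, section 10.1.1), and replacement kits are available (section 8.5).
- The events are not lost to the sponsor. Every PTC goes on a form (section 10.4.1), patients who leave early still complete Visit 102, and the disposition table has a line for patients enrolled without being treated.
- The sub-study is descriptive, with no formal sample size and no success threshold, so no decision rule turns on the count.
- An attempted-use set departs from protocol section 11.4.2.1. It also needs a grouping rule, because a never-dosed patient has no treatment actually received.

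These points limit the size of the problem and add a little to the cost of the fix, but they do not remove the problem. A failure recorded on a form and in the e-CRF would still be absent from the tables that report the primary endpoint. The unrecorded difference between SAP and protocol remains whatever the numbers are.

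A reader might infer that a patient enters the analysis set only if the device worked, or that anyone whose attempts all failed is removed. The documents do not say that. The condition is one received dose at any time in the 12 weeks, and a patient whose only failures concerned the shield after a full injection meets it.

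**Conclusion.** The point holds in a limited form. On a literal reading, the SAP leaves out of the PTF, PTC and FDD tables any sub-study patient who never received a full dose by PFS-S. The protocol leaves out only those who received no drug at all. The SAP's narrowing is not recorded.

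The effect on the results is probably very small: practically zero if patients go on to later injections, and about 0.6 to 6 of 120 only in the extreme case where every patient leaves after a first no-delivery failure, at assumed rates of 0.5% to 5%. A reader might infer a material bias in the primary count. The documents support no such figure, because they state neither a failure rate nor how often a failure leads to exit. What they do support is the direction: the exclusion can only lower the failure count.

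**What to change.** 1. Align the sub-study safety population in SAP Appendix K with protocol Appendix R, section 11.3, by restoring partial doses.
2. Analyse PTF, PTC and FDD in all enrolled sub-study patients with at least one attempted PFS-S injection, where an attempt is any use recorded in the injection diary, whether or not drug was delivered.
3. Where no dose was delivered, group the patient by the dose allocated at Visit 101.
4. Keep the dosed populations for the adverse-event and PK summaries.
5. Record the change from protocol section 11.4.2.1 in the SAP's list of modifications.

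The cost is a short SAP edit: one population definition, a definition of an attempt, a grouping rule and a note of the departure from the protocol. The diary and complaint data are already collected at Visit 102, so no new data, visits or patients are needed.

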## **Demographics and baseline characteristics**

Demographics and baseline characteristics will be presented for the enrolled patients in this sub-study.

## **Extent of investigational product exposure and compliance**

The extent of study treatment exposure and compliance will be assessed and summarized by actual treatment received within the safety population.

The duration of IMP exposure is defined as: last dose date – first dose date at D1 + 14 days (regardless of unplanned intermittent discontinuations).

Treatment compliance to the IMP is defined as the actual number of doses received compared to the scheduled number of doses during the treatment period. Treatment compliance during the treatment period in the sub-study will be summarized descriptively.

## **Efficacy (Device) analysis**

Data will be described for the 12 weeks of this sub-study using the safety population. The efficacy analyses will be performed using descriptive statistics and presented by treatment group.

## ***Primary endpoint***

The primary endpoint is the number of validated PFS-S-associated PTFs.

The injection diary will include specific questions about PTCs. The person performing each sub-study injection will record the answers to these questions in the diary each time he/she performs an injection with a PFS-S.

The questions include:

1. Were you able to remove the cap?
  - Yes
  - NoIf no, please describe / explain:
2. Was the needle safety system activated?
  - Yes
  - NoIf no, please describe / explain:
3. Did the safety system entirely cover the needle?
  - Yes

- No  
If no, please describe / explain:

At Week 12 (Visit 102), the Investigator will review the diary, confirm with the patient whether there are any problems associated with the use of PFS-S and record the responses in the e-CRF.

If the answer is “no” to any of the questions stated in the diary, the patients will be asked to provide further details of the complaint and a PTC form will be completed by the investigator. The PTC form and the PFS-S associated with PTC will be sent to the Sponsor following the pre-defined process. The sponsor will validate or invalidate the occurrence of a PTF. If the PTF is ruled out, the event is considered as a failed drug delivery (FDD) that is defined as patient’s failure to administer the full dose at a given attempt.

In addition, another question will be asked in the diary to confirm whether the person who performed the injection was trained:

4. Was the person who performed the injection the person who was trained by the site staff?
  - Yes
  - No

### ***Secondary endpoints***

- Number of PTCs
- Number and percentage of patients with PTFs
- Number and percentage of patients with PTCs
- Number and percentage of patients with FDDs

